6.10.2 Clinical Laboratory Parameters

Clinical safety laboratories (CBC, Chemistries, Creatine Kinase, Free Serum SA Levels, and Pregnancy tests) will be assessed during Part I of this study at baseline and the Part I termination visit. For subjects who roll-over from study UX001-CL201 the baseline clinical laboratory values may be derived from the last visit (week 48, or termination visit) in UX001-CL201, prior to participation in UX001-CL202.

Clinical safety laboratories (CBC, Chemistries, Creatine Kinase, and Free Serum SA Levels) will be assessed during Part II of this study at the Screening/Baseline and Months 1, 3, 6, 12, 18, 24, 30, 36, and termination visits. Pregnancy testing will be completed in Part II at the Screening/Baseline and Months 12, 24, and termination visits. For subjects who roll-over

from study UX001-CL201 and participate in Part I of this study the baseline clinical laboratory values may be derived from the last visit in Part I (Part I termination visit). For Treatment Naïve Subjects enrolled directly into Part II the baseline values will be the Screening/Baseline visit for these subjects.

Laboratory data will be monitored for safety and will be listed by subject. No descriptive information will be compiled for clinical laboratory data.

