7.6.2 Safety Measures

The safety measures in this study are:

- Incidence and frequency of AEs and SAEs
- Clinically significant changes from baseline in vital signs, physical and neurological examination findings and laboratory evaluations
- Interval history, including reported symptoms of increasing muscle weakness or pain, and incidence of falls

The analyses of safety will include all subjects who receive any study drug at any time during the study and provide any post-treatment safety information. Safety data will be periodically reviewed by the DMC.

For the safety analysis, the incidence and frequency of AEs and SAEs will be evaluated. All AEs will be coded using the Medical Dictionary for Regulatory Activities (MedDRA). The incidence and frequency of AEs will be summarized by System Organ Class (SOC), Preferred Term (PT), relationship to study drug, and severity for each treatment group. A by-subject listing will be provided for those subjects who experience a SAE, including death, or experience an AE associated with early withdrawal from the study or study drug.

Clinical laboratory data will be summarized by the type of laboratory test. The frequency and percentage of subjects who experience abnormal clinical laboratory results (i.e., outside of reference ranges) and/or clinically significant abnormalities after study drug administration will be presented for each clinical laboratory measurement. For each clinical laboratory measurement, descriptive statistics will be provided for Baseline and all subsequent post-treatment scheduled visits. Changes from Baseline to the post-treatment visits will also be provided. Descriptive statistics of vital signs, imaging assessments, and concomitant medications will also be provided in a similar manner.

The SAP will provide additional details on the planned statistical analysis.

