1 INTRODUCTION

This document presents a statistical analysis plan (SAP) for Ultragenyx Pharmaceutical, Inc. Protocol UX001-CL202 (*An Open-label Phase 2 Extension Study to Evaluate the Long Term Safety and Efficacy of Sialic Acid-Extended Release (SA-ER) Tablets and Sialic Acid-Immediate Release (SA-IR) Capsules in Patients with GNE Myopathy or Hereditary Inclusion Body Myopathy*).

Reference materials for this statistical plan include the Protocol UX001-CL202 (Original: 01 March 2013, Amendment #1: 02 October 2013), UX001-CL202 Case Report Forms (24 July 2013), feeder study Protocol UX001-CL201 and the SAP for UX001-CL201 (05 November 2013: Week 48 Analysis). Study UX001-CL202 is an Open-Label extension study and treatment is not blinded. Subjects completing 48-week in study UX001-CL201 are eligible to continue treatment under this open-label extension protocol testing an increased dose of SA. Additional GNE Myopathy subjects will be enrolled to assess the safety and efficacy of SA-ER/SA-IR in a treatment naïve population. Ultragenyx Pharmaceutical is conducting UX001-CL202 in two parts:

- Part I of the study will provide additional information on the long-term safety and efficacy of 6g/day SA ER;
- Part II of the study will assess the safety and efficacy of 1.5 g of SA-ER / 1.5 g of SA-IR treatment 4 times per day (12g/day SA-ER/SA-IR total dose) for 6 months. If reasonable efficacy and safety are demonstrated at the interim analysis at 6 months post initiation of part II, the subjects may continue therapy for up to 36 months.

The statistical plan described hereafter is an *a priori* plan. The SAP will be finalized and approved prior to completing inferential or descriptive analyses of data pertaining Ultragenyx Pharmaceutical, Inc. Protocol UX001-CL202. Statistical Analysis programming may occur as study data accumulate in order to have analysis programs ready at the time the study finishes. For the reasons stated herein the conduct of the study in the field is considered to be independent of any study outcome that might materialize upon enactment of the currently proposed statistical analysis plan.

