3 STUDY DESIGN

As background for the statistical methods presented below, this section provides an overview of the study design and plan of study execution. The protocol (plus protocol amendment) is the definitive reference for all matters discussed in what follows.

UX001-CL202 open-label extension study will assess the long term safety and efficacy of SA ER/SA-IR treatment over a period of approximately 36 months, or until marketing approval or program termination by Ultragenyx. In Part I of the study, approximately 46 subjects will be enrolled following successful completion of the UX001-CL201 study. The Baseline visit will be conducted in conjunction with the UX001-CL201 Week 48 study visit to avoid treatment disruption. Enrollment will take place after all UX001-CL201 Week 48 study assessments have been completed and the investigator has determined the subject meets all eligibility criteria. Data collected at the UX001-CL201 Week 48 visit will serve as the Baseline data for Part I of this protocol. Following the signing of informed consent at the Baseline visit, each subject will be dispensed a 6-week supply of study drug. Throughout the Part I Treatment Period of the study, all subjects will continue to take four 500 mg SA-ER tablets orally three times per day (TID), in the morning, early evening, and at bedtime (qHS), for a total dose of 6g/day. The Part I Termination Visit will also serve as the Baseline Visit for Part II of the study. However, for completion of the analysis with integrated information from UX001-CL201 subjects the baseline may be defined as the week 48 visit from UX001-CL201, or other such baselines from key time points in the UX001-CL201 study as may be defined for selected analyses to examine clinical endpoints.

Beginning with the Part II-Baseline Visit, all subjects currently enrolled in Part I will crossover to the SA-ER/SA-IR dosing regimen. An additional 10 treatment naive GNE Myopathy subjects will be enrolled into Part II of the study. The additional subjects will provide an assessment of SA-ER/SA-IR treatment in SA naïve subjects able to walk at least 200 meters (and < 80% predicted) in a screening 6 Minute Walk Test (6MWT). Throughout the 36-month Part II Treatment Period, all subjects will be administered 1.5g SA-ER and 1.5g SA-IR orally four times per day (QID), in the morning, afternoon, early evening, and qHS, for a total SA dose of 12g/day.

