6.5.1 Changes in Analysis in Comparison to Study Protocol

The analyses described in this analysis plan are consistent with the intended analyses described in the study protocol. In addition results from the UX001-CL201 study, both the Week 24 and Week 48 analyses, will be utilized as baseline information to explore and compare the various dosing combinations and trends in efficacy parameters, between the UX001-CL201 randomized feeder study and the UX001-CL202 extension study.

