6.10.3 Vital Signs

Vital signs (Blood Pressure, respiratory rate, heart rate) will be assessed during Part I of this study at baseline and the Part I termination visit. For subjects who roll-over from study UX001-CL201 the baseline vital sign values may be derived from the last visit (week 48, or termination visit) in UX001-CL201, prior to participation in UX001-CL202.

Vital signs (Blood Pressure, respiratory rate, heart rate) will be assessed during Part II of this study at the Screening/Baseline and Months 1, 6, 12, 18, 24, 30, 36, and termination visits. For subjects who roll-over from study UX001-CL201 and participate in Part I of this study the baseline vital sign values may be derived from the last visit in Part I (Part I termination visit). For Treatment Naïve Subjects enrolled directly into Part II the baseline values will be the Screening/Baseline visit for these subjects.

Vital signs data will be monitored for safety and will be listed by subject. No descriptive information will be compiled for vital signs data.

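### The SAP rules out the laboratory and vital-sign summaries that section 7.6.2 of the current protocol says will be provided

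*SAP*

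**What the plan says.** SAP 6.10.2 has laboratory data monitored and listed by subject, then adds: "No descriptive information will be compiled for clinical laboratory data". SAP 6.10.3 does the same for vital signs: "No descriptive information will be compiled for vital signs data". The table list in SAP 8.1 agrees. Safety Tables 8 to 14 cover falls and treatment-emergent adverse events (TEAEs). The only laboratory quantities with a summary table are free serum SA (Table 483) and CK (Table 495).

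Protocol 7.6.2 commits to more. For each laboratory measurement, "descriptive statistics will be provided for Baseline and all subsequent post-treatment scheduled visits"; changes from Baseline, and the frequency and percentage of subjects with out-of-range or clinically significant results, are also to be given. For the rest: "Descriptive statistics of vital signs, imaging assessments, and concomitant medications will also be provided in a similar manner". The same section names as a safety measure: "Clinically significant changes from baseline in vital signs, physical and neurological examination findings and laboratory evaluations".

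Two other parts of the SAP lean the protocol's way. Section 5.3, whose Table 5 includes the laboratory tests and vital signs, has the safety variables summarised for each of Parts I and II. Section 6.10 opens by saying that safety analyses generally use descriptive summaries as well as graphs and listings.

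**The concern.** A programmer cannot follow both documents, or all of the SAP. Following 6.10.2, 6.10.3 and 8.1 means that the protocol's laboratory and vital-sign tables are not produced.

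Safety comes first among the protocol's objectives, and Part II is the first time that GNE Myopathy subjects receive the 12 g/day SA-ER/SA-IR combination. An abnormality that an investigator reports as an adverse event still reaches the TEAE tables. A modest shift across the whole group, with few individuals out of range, does not. It would be found only by reading listings, in shift tables that the SAP makes optional and post hoc (6.5.4), in comparisons run on request (6.10.9), or in committee review. Under 6.10.9 a p-value for a laboratory test could even be reported without the by-visit means behind it.

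**Working it through.** The main check compares texts. Neither document gives a calculation on this point to reproduce.

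**1. The passages side by side**

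| Output | Protocol 7.6.2 | SAP 6.10.2, 6.10.3 and 8.1 |
|---|---|---|
| Laboratory statistics by visit | Will be provided, each measurement | None, except CK and free SA |
| Laboratory change from Baseline | Will be provided | None, except CK and free SA |
| Abnormal-result frequencies | Will be provided | None planned; post-hoc shift tables possible |
| Vital-sign statistics | Will be provided, in a similar manner | None |

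**2. What has no planned group summary (counted in SAP Table 5)**

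- Haematology: 17 entries less the WBC differential heading = 16.
- Chemistry: 21 entries less CK, which is summarised under 6.7.13 = 20.
- Total: 16 + 20 = 36 tests.
- Vital signs: systolic and diastolic pressure, heart rate, respiratory rate, temperature = 5.
- Urinalysis: scheduled in Part I only (SAP Tables 1 and 2).

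**3. What a by-visit table adds to a listing (illustration)**

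Assumptions, none from the documents: normally distributed values, a reference range covering the central 95%, and a mean rise of 0.5 SD. The documents supply the planned 46 rollover subjects.

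- Expected number above the upper limit before the shift: 46 × [1 − Φ(1.96)] = 46 × 0.0250 = 1.15.
- After the shift: 46 × [1 − Φ(1.46)] = 46 × 0.0721 = 3.32.
- SD of change in SD units = √[2(1 − ρ)]: 1.00 at ρ = 0.5 and 0.63 at ρ = 0.8.
- Half-width of the 95% CI = t(45) × SD / √46: 0.297 and 0.188.
- Mean change 0.5 SD, 95% CI 0.20 to 0.80 (ρ = 0.5) or 0.31 to 0.69 (ρ = 0.8).

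About two extra high values among 46 subjects are easily missed in a listing. The mean change would be plain in a table.

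**4. Secondary: exposure behind the TEAE percentages**

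SAP 6.10.1 shows the percentage of subjects with TEAEs on 6 g/day and on 12 g/day. Inputs: 46 rollover and 10 treatment-naïve subjects; Part I at most about 12 weeks; first Part II analysis at 6 months (24 to 26 weeks).

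- 6 g: 46 × 12/52 = 10.6 patient-years at most.
- 12 g: 56 × 24/52 = 25.8, or 56 × 26/52 = 28.0.
- With the same constant rate r per patient-year on both doses (assumed), the proportion with an event is 1 − exp(−r × weeks/52). At r = 0.5 this is 10.9% at 12 weeks against 20.6% to 22.1% at 24 to 26 weeks.
- Over r = 0.05 to 1.0 the ratio of percentages is 1.8 to 2.2. If events cluster early after each dose starts (assumed Weibull shape 0.5), it is 1.3 to 1.5.

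**The case against.** **Protocol version.** The SAP names as its references the Original protocol of 01 March 2013 and Amendment 1 of 02 October 2013. The protocol in hand is later, and Amendment 2 revised its statistical section. SAP 6.5.1 states: "The analyses described in this analysis plan are consistent with the intended analyses described in the study protocol". A reader might infer that this was false when written, or that a departure was concealed. The documents do not support that, because the Amendment 1 text of 7.6.2 is not available. The reasons logged for the Amendment 2 change do not mention laboratory or vital-sign summaries, but that is not proof. This objection stands and limits the claim to a mismatch with the current protocol.

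**Force of the protocol text.** Protocol 7.6 leaves detailed methods to the SAP and describes what follows as a guide. Its vital-sign sentence also mentions imaging, which neither schedule contains, so it cannot be restored word for word. Both are fair, and amending the protocol is a legitimate remedy. A guide may be refined, but a reversal should be stated. The SAP sentence "The protocol (plus protocol amendment) is the definitive reference for all matters discussed in what follows" adds little, since it introduces a background overview of the design.

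**Further SAP contradictions.** A reader might infer that the rules in 6.5.4 for continuous laboratory summaries and in 6.5.5 for early-termination safety data have nothing to act on. They do, because CK and free serum SA are summarised. A reader might also see contradictory baselines within 6.10.2. In fact it separates Part I (last UX001-CL201 visit) from Part II (Part I termination visit); what is left is permissive wording and the silence of 5.3 on the Part II rule. Nor do Months 18 and 30 in the 6.10.2 visit list prevent the tables, since visits without data give empty rows.

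**The illustration.** The 0.5 SD shift is arbitrary, and an out-of-range table would show the same small rise in counts. The gain comes from the by-visit mean change.

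**TEAE percentages.** The protocol asks only for incidence and frequency. The SAP supplies number and percent, summarises doses administered by treatment group (6.6.2), plans no inferential safety tests and analyses subjects as treated. That is enough to make person-time optional.

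**Conclusion.** On this point the SAP does not match the current protocol, nor its own 5.3 and 6.10, and it should be changed. The text comparison needs no assumption. The size is 36 haematology and chemistry tests, Part I urinalysis and 5 vital signs without a planned group summary. This matters for the safety read-out, but safety is not left unmonitored.

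The TEAE point is a minor improvement. Each dose's percentage is valid alone; side by side, part of any difference reflects length of observation. The patient-years are planned figures. Part I length varied, some rollovers went straight to Part II, and the current protocol sets its interim analysis for when a majority reach Month 6. It also returns many rollovers to 6 g/day in Part III, which this SAP does not cover. The fold-differences rest on assumed rates.

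**What to change.** - Replace the two sentences in SAP 6.10.2 and 6.10.3 with the protocol 7.6.2 summaries: by-visit statistics and change from Baseline for laboratory tests and vital signs, and frequencies of abnormal results for laboratory tests. Add the tables to 8.1.
- If the sponsor intends to omit them, declare and justify this in SAP 6.5.1 and amend protocol 7.6.2. Either way, check the SAP against the current protocol and settle the reference to imaging.
- Reconcile the laboratory visits in 6.10.2, which include Months 18 and 30, with SAP Table 2, which schedules neither.
- Make 5.3 state the same Part II rollover baseline as 6.10.2, in firm wording, and say what applies to rollovers who skipped Part I.
- Optional: attribute each TEAE to the dose at onset or worsening, and give patient-years and exposure-adjusted incidence with 95% CIs beside the percentages.

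The cost is SAP wording and a limited set of standard tables from data already collected. The drawback is more output. Exposure-adjusted rates would not make 6 g and 12 g a controlled comparison, because the dose order is fixed and the same rollovers appear in both columns.

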6.10.3 Vital Signs

Vital signs (Blood Pressure, respiratory rate, heart rate) will be assessed during Part I of this study at baseline and the Part I termination visit. For subjects who roll-over from study UX001-CL201 the baseline vital sign values may be derived from the last visit (week 48, or termination visit) in UX001-CL201, prior to participation in UX001-CL202.

Vital signs (Blood Pressure, respiratory rate, heart rate) will be assessed during Part II of this study at the Screening/Baseline and Months 1, 6, 12, 18, 24, 30, 36, and termination visits. For subjects who roll-over from study UX001-CL201 and participate in Part I of this study the baseline vital sign values may be derived from the last visit in Part I (Part I termination visit). For Treatment Naïve Subjects enrolled directly into Part II the baseline values will be the Screening/Baseline visit for these subjects.

Vital signs data will be monitored for safety and will be listed by subject. No descriptive information will be compiled for vital signs data.

6.10.4 Medical History

Medical History for subjects who roll-over from study UX001-CL201 will be carried forward from the UX001-CL201 study.

Medical History (and Interval History) will be assessed during Part II of this study at the Screening/Baseline and Months 1, 6, 12, 18, 24, 30, 36, and termination visits. For Treatment Naïve Subjects enrolled directly into Part II medical history (and interval history) will be assessed at the Screening/Baseline visit for these subjects.

A detailed medical history will be obtained at Screening and presented descriptively by treatment group. The medical history will solicit information on any prior or existing medical conditions that might interfere with study participation or safety. Medical History information from subjects who participate in Part I of this study and roll-over from UX001-CL201 will be carried forward from the UX001-CL201 study. For Treatment Naïve Subjects enrolled directly into Part II the medical history will be obtained at the Screening/Baseline visit for these subjects.

Medical history results for all subjects in the safety population will be reported in listing format, identifying those subjects carried over from UX001-CL201 and those Treatment Naïve Subjects enrolled into Part II.

6.10.5 Interval History

Interval History will be assessed during Part I of this study at baseline and the Part I termination visit. For subjects who roll-over from study UX001-CL201 the baseline interval history values may be derived from the last visit (week 48, or termination visit) in UX001-CL201, prior to participation in UX001-CL202.

Interval History will be assessed during Part II of this study at the Screening/Baseline and Months 1, 6, 12, 18, 24, 30, 36, and termination visits. For subjects who roll-over from study UX001-CL201 and participate in Part I of this study the baseline interval values may be derived from the last visit in Part I (Part I termination visit). For Treatment Naïve Subjects enrolled directly into Part II the baseline values will be the Screening/Baseline visit for these subjects.

Each interval history is intended to record any signs, symptoms, or events (i.e., falls) experienced by the subject since the prior study visit that are not related to study procedure(s) performed at prior study visits or study drug. Interval history may include exacerbation or improvement in existing medical conditions (including the clinical manifestations of HIBM) that might interfere with study participation, safety, and/or positively or negatively impact performance of functional assessments. Interval history may identify under-reported AEs.

Interval history for all subjects in the safety population will be reported in listing format, identifying those subjects carried over from UX001-CL201 and those Treatment Naïve Subjects enrolled into Part II.

The number of falls experienced by subjects in Part I (6g/day SA-ER) and in Part II (12g/day SA-ER/SA-IR) treatment groups will be evaluated at each study time point using descriptive statistics.

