^d For SA naïve subjects, medical history (including a detailed GNE Myopathy disease-specific history) will be reviewed at the Screening/Baseline visit. Interval history for all subjects will include any signs, symptoms, or events (e.g., falls) experienced by the subject since the prior study visit that are not related to study procedure(s) performed at prior study visits or study drug. Interval history may include exacerbation or improvement in existing medical conditions (including the clinical manifestations of GNE Myopathy) that might interfere with study participation, safety, and/or positively or negatively impact performance of functional assessments.

^e The physical examinations at all study visits will be complete.

^f Portions of the HHD, 6MWT, walking speed and weighted arm lift testing sessions may be videotaped to monitor administration technique and assess qualitative changes in function. Subject identity will be protected by blurring out the facial area in the video.

^g Trough levels of free SA in serum.

^h Adverse Events will be collected after subject signs Informed Consent form.

ⁱ Study drug will be dispensed at scheduled treatment visits; additional study drug will be shipped directly to subjects between visits on a monthly basis.

^j Phone calls will be placed to each subject at least once between each study visit to assess treatment compliance with the dosing regimen. Additional telephone contacts with the subject may be placed as needed.

^k Subjects who complete this study and are eligible may enroll in the UX001-CL302 open-label extension study. The Month 36 Visit is considered the end of study visit for subjects who are eligible and chose to participate in the open label extension study.

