7.5.4.2 Interval History

Each interval history is intended to record any signs, symptoms, or events (e.g., falls) experienced by the subject since the prior study visit that are not related to study procedure(s) performed at prior study visits or study drug. Interval history may include exacerbation or

improvement in existing medical conditions (including the clinical manifestations of GNE Myopathy) that might interfere with study participation, safety, and/or positively or negatively impact performance of functional assessments. Interval history may identify under-reported AEs, and will be collected at the study visits indicated in the Schedule of Events ([Table 2.1](#) and [Table 2.2](#)).

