6.7.5 Efficacy Analysis: Muscle Strength - Hand Held Dynamometry (HHD)

The hand held dynamometry (HHD) assessment is completed in UX001-CL202 at the Part II time points of Screening/Baseline (last visit in Part I), months 3, 6, 12, 18, 24, 30, 36, and the termination visit (Table 2). The HHD parameters will be summarized into composite scores and GEE analyses will be performed.

HHD Upper Extremity (UE) Composite Score

HHD UE composite scores will be used to evaluate change in upper extremity muscle strength. HHD UE composite scores achieved for the 12g/day SA-ER/SA-IR dosing group at each study time point will be evaluated using descriptive statistics.

A GEE model (see Section 6.7.2) will be completed for the week 24 (6 month) analysis and will include the visits from Part II of UX001-CL202 (Months 1 to 6) accounting for time on the 12g/day SA-ER/SA-IR treatment with subjects who cross-over from treatment administered in UX001-CL201 (Table 3). The primary model will incorporate the treatment groups defined in the planned comparisons (Table 8).

HHD Lower Extremity (LE) Composite Score

HHD LE composite scores will be used to evaluate change in lower extremity muscle strength. HHD LE composite scores achieved for the 12g/day SA-ER/SA-IR dosing group at each study time point will be evaluated using descriptive statistics. The same modelling strategy applied for the HHD UE will be applied for the HHD LE Composite score.

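### Falls are recorded back to the prior study visit but not at every visit, so the planned fall counts are incomplete or span unequal periods, depending on how sites read the look-back

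*SAP*

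**What the plan says.** SAP 6.10.5 defines the look-back: "Each interval history is intended to record any signs, symptoms, or events (i.e., falls) experienced by the subject since the prior study visit". Protocol 7.5.4.2 uses the same look-back, and so does footnote d to protocol Table 2.2, which covers Parts II to IV: "Interval history for all subjects will include any signs, symptoms, or events (e.g., falls) experienced by the subject since the prior study visit".

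The same SAP section schedules interval history in "Part II of this study at the Screening/Baseline and Months 1, 6, 12, 18, 24, 30, 36, and termination visits". SAP Table 2, which the SAP says repeats protocol Table 2.2, also has visits at Months 3, 9, 15, 21, 27 and 33. Those columns carry adverse event checks and drug dispensing but no interval history.

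Falls matter to the plan. Protocol 7.6.2 lists among the safety measures: "Interval history, including reported symptoms of increasing muscle weakness or pain, and incidence of falls". In SAP 8.1 the number of falls is the only interval-history item with its own planned table (item 8 in that list, not the Table 8 of planned comparisons in SAP 6.7.1). For the analysis, SAP 6.10.5 says that the number of falls in the Part I (6 g/day) and Part II (12 g/day) "treatment groups will be evaluated at each study time point using descriptive statistics". It gives no observation window, rate or exposure adjustment.

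**The concern.** A look-back to the prior visit gives continuous coverage only if the question is asked at every visit. Here it is skipped at six scheduled visits. At Month 6 the prior visit is Month 3, and at Month 12 it is Month 9, so the stretch before each skipped visit belongs to no interval history.

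A site can apply the wording as written, and the falls table is then incomplete. Or it can ask back to the last interval history, and the counts then cover periods of different length. The plan does not say which, and it summarises raw counts either way. Differences between time points, or between the 6 g/day and 12 g/day periods, could then reflect the length of look-back and not the subjects' condition.

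Month 3 deserves notice. Muscle strength is tested at "months 3, 6, 12, 18, 24, 30, 36, and the termination visit", and the walking and arm-lift tests are also done at Month 3. Protocol 7.5.4.2 says interval history may cover events that affect performance on functional assessments, yet none is taken at that visit.

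**Working it through.** The plan gives no figure to reproduce. The check is interval arithmetic on the visit schedule.

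**Inputs**
- Scheduled visits (SAP Table 2): 0, 1, 3, 6, 9, 12, 15, 18, 21, 24, 27, 30, 33, 36 months, then Termination four weeks after last dose, taken as Month 37.
- Interval history (SAP 6.10.5): 0, 1, 6, 12, 18, 24, 30, 36 months and Termination.
- Literal window = visit month minus preceding scheduled visit. Alternative window = visit month minus preceding interval history.

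| Interval history at | Preceding visit | Literal window (months) | Since last interval history (months) |
|---|---|---|---|
| Month 1 | Baseline | 1 | 1 |
| Month 6 | Month 3 | 3 | 5 |
| Months 12, 18, 24, 30, 36 (each) | Months 9, 15, 21, 27, 33 | 3 | 6 |
| Termination | Month 36 | 1 | 1 |

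**Coverage, literal reading**
- To Month 36: 1 + 6 × 3 = 19 months covered; 36 − 19 = 17 uncovered; 17/36 = 47.2%. The gaps are Months 1–3, 6–9, 12–15, 18–21, 24–27 and 30–33 (2 + 5 × 3 = 17).
- Including Termination: 17/37 = 45.9%.
- To the Month 6 analysis: 1 + 3 = 4 months covered; 2/6 = 33.3% uncovered.

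**Coverage, alternative reading**
- 1 + 5 + 5 × 6 = 36 of 36 months, no gap.

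**Effect on raw counts at a constant fall rate**
- Expected count = rate × window, so the ratio between visits does not depend on the rate. Month 6 to Month 1 is 3/1 = 3 (literal) or 5/1 = 5 (alternative).
- For illustration, at an assumed 0.5 falls per month, Months 1, 6 and 12 show 0.5, 1.5 and 1.5 falls (literal) or 0.5, 2.5 and 3.0 (alternative). At 0.1 per month they show 0.1, 0.3 and 0.3, or 0.1, 0.5 and 0.6. At 1 per month they show 1, 3 and 3, or 1, 5 and 6.
- Months 12 to 36 have equal windows on both readings. Month 6 matches them only on the literal reading.

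**Part I**
- Interval history is taken at Baseline and the Part I Termination Visit. The period runs up to about 12 weeks, but the note to SAP Figure 1 says participation varied by subject and some rollover subjects went straight to Part II. There is no common Part I window to set against Part II.

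**Sensitivity**
- If Months 9, 15, 21, 27 and 33 were not study visits, the literal gap would fall to Months 1–3 (2/36 = 5.6%), with windows of 1, 3, then 6 months. The documents point the other way: these visits have a ±14-day window, adverse event checks and drug dispensing, and protocol 7.4.2 places dispensing in clinic.
- With ±14 days at each end and 30.44 days per month, a nominal 3-month window can run from (91.3 − 28)/30.44 = 2.1 to (91.3 + 28)/30.44 = 3.9 months.

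**The case against.** The best answer is that interval history is not the only way to find a fall. Protocol 7.5.4.8 has subjects asked about adverse events at every visit, and protocol 8.5.1 defines an adverse event broadly enough to include an injurious fall. Month 3 also has a concomitant medication check. This stands: a reader might infer that falls go unasked about for half the study, or that an injury before the Month 3 tests is never recorded, and the documents do not support either. What remains is narrower. No text requires every fall to be an adverse event, and none feeds falls reported as adverse events into the falls table. The calls between visits are specified for treatment compliance.

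Second, the name itself suggests a history taken from one interval history to the next, and the case report form, which may settle the wording, is not shown. Sites may well ask that way. That closes the gap but produces the 1, 5, 6-month windows.

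Third, SAP 6.10 plans safety summaries as descriptive only and does not say the periods are treated as equal. No planned test is distorted, which limits the harm, but a descriptive table of counts without their windows can still mislead.

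Two further inferences should be resisted. The 47% gap and the six-fold spread of windows (1 against 6 months) belong to different readings and cannot both occur; the literal spread is three-fold. A trend across Months 12 to 36 is not an artefact of window length on either reading.

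**Conclusion.** The concern holds in limited form. Following the stated rule leaves 17 of 36 months of Parts II to IV, and 2 of the first 6, outside every interval history. This rests on the literal look-back and on Months 9 to 33 counting as study visits, which the schedule supports. If sites ask since the last interval history, there is no gap.

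On both readings the Month 1 and Termination windows (1 month) differ from Month 6 (3 or 5 months), and Part I has no common window. Raw counts across those points, and Part I against Part II, are therefore not comparable. Counts at Months 12 to 36 can be compared with each other, provided sites use one reading.

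The finding concerns the interval-history record and the table built on it, not all capture of falls. SAP 6.10.5 describes only Parts I and II, but its Part II runs 36 months, and footnote d to protocol Table 2.2 applies the same look-back to Parts II to IV.

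**What to change.** In protocol 7.5.4.2, footnote d to Table 2.2 and SAP 6.10.5, make the look-back contiguous in one of two ways:
- Reword it to run from the last interval history. This changes text only, but recall reaches 6 months.
- Ask the falls question at each existing visit, including Month 3 where the performance tests are done. Windows become 1, 2 and then eleven of 3 months (1 + 2 + 33 = 36), with 1 month at Termination. Recall is at most 3 months. The cost is one short question at six visits that already take place.

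Windows stay unequal under either option. In SAP 6.10.5 and the planned falls table, replace raw counts per time point with falls per person-month of look-back, computed from each subject's actual dates, and show the window beside each estimate. This also deals with the variable length of Part I. For data already collected, state which look-back the case report form used. The cost is small text edits and one changed table shell, with no new visits.
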